### 3.2.3 Experimental Design and Analysis Methods

This study is a prospective, unblinded, multi-center, worldwide clinical study designed to evaluate the procedure and/or device related peri-procedural stroke rate within 30 days of an ablation procedure with the Phased RF System. The study will be considered successful if the primary objective is met. A single decision regarding study success will be made once all subjects with a Phased RF ablation procedure have had the opportunity for a reablation procedure (completed the 6-month visit) or completed the 30-day post-reablation visit if a reablation is required. Alternatively, the study may stop early for futility if more than six (6) procedure and/or device related peri-procedural strokes occur prior to completing enrollment.

For computing the peri-procedural stroke rate, the denominator will include:

1. All subjects with at least one ablation procedure attempt where at least one of the Phased RF catheters was deployed into the left atrium with Phased RF energy delivered and have at least 30 days of post-procedural follow-up, AND
2. Subjects with a procedure and/or device related peri-procedural stroke as classified by the CEC within 30-days of a Phased RF procedure regardless of the subject’s follow-up duration.

The numerator for the stroke rate will be all subjects included in the denominator that had a procedure and/or device related stroke as classified by the CEC with a symptom onset date within 30 days of a Phased RF ablation procedure. The null hypothesis will be rejected in favor of the alternative if the observed stroke rate is less than 1.8% and the exact one-sided upper 95% confidence interval is less than 3.5%.

Additionally, a one-sided exact p-value will be computed for comparing the observed stroke rate to the performance goal of 3.5%.

[REDACTED]

### 3.2.4 Sample Size Methods and Assumptions

[figure not shown]
A sample size of 300 subjects completing the 30-day post procedure follow-up visit and having the opportunity for a reablation procedure (i.e. completing the 6-month follow-up visit) or having a reablation procedure and completing the 30-day post-reablation visit provides at least 80% power to test the primary study hypothesis given the following assumptions:

1. One-sided type I error rate of 0.05
2. Exact test of a binomial proportion versus a fixed performance goal of 3.5%
3. Observed stroke rate must be less than 1.8%.
4. Assumed true stroke rate is 1.3%

Figure 1 displays the power of the study to meet its primary objective when the true stroke rate ranges from 0.1% to 3.5% and 300 subjects complete the 30-day post-ablation (or reablation) visit and have had the opportunity for a reablation procedure. Specifically, the study has 90% power if the true stroke rate is 1%, 80% power if the true stroke rate is 1.3%, and 55% power if the true stroke rate is 1.8%. Figure 1 also demonstrates that the type I error is less than 5% when the true stroke rate is 3.5%.

Assuming an annualized attrition rate of 10%, a uniform reablation rate of 30% within 180 days of the index ablation procedure, and a conservative 11% pre-procedure attrition rate up to 350 enrolled subjects will be required to ensure that at least 300 subjects complete the 30-day post ablation follow-up visit and have the opportunity for a reablation procedure or have a reablation procedure and complete the 30-day post-reablation procedure visit.

Figure 1: Study Power versus True Stroke Rate

Note: Power curve computed using exact binomial method.

### 3.2.5 Determination of Subjects for Analysis

All subjects with at least one attempted ablation procedure with the Phased RF system where at least one investigational catheter was deployed into the left atrium (i.e. placed in the left atrium with Phased RF energy delivered) and have completed at least 30 days of post-procedure follow-up will be included in the analysis. Additionally, all subjects with a procedure and/or device related stroke as classified by the CEC with a symptom onset date within 30 days of a procedure where a Phased RF catheter was deployed in the left atrium will be included in the analysis regardless of whether the subject has less than 30 days of post-procedural follow-up.

In the rare instance where a subject has a non-investigational ablation catheter placed in the left atrium, the subject will be excluded from the analysis of the primary objective. However, a summary of all peri-procedural adverse events (AEs) will be provided for any subject excluded from the primary analysis.

### 3.2.6 Missing Data

The impact of missing data on the analysis of this objective is expected to be small since only a 30 day post-ablation follow-up period is required. However, missing data could arise if a subject undergoes a Phased RF ablation procedure, does not have procedure and/or device related peri-procedural stroke, and exits the study prior to their 30 day post-procedure visit. These subjects will not be included in the primary analysis cohort, but a tipping point analysis will be employed to determine the impact of the missing data on the observed stroke rate should the issue of missing data arise.

Another potential source of missing data comes from subjects that do not have a stroke following the index procedure, but exit the study following the 30-day post index ablation visit, but prior to 6 months post the index procedure (allowed reablation period). These subjects are included in the primary analysis as not having a stroke since no stroke was observed following the index ablation procedure. However, a tipping point analysis will be conducted to determine the plausibility these subjects could change the outcome of the

study across a range of reablation rates and reablation stroke rates. Sample R code for performing the modified tipping point analysis can be found in the Appendix.

### **3.2.7 Pre-specified Subgroup Analyses**

The procedure and/or device related stroke rate will be displayed separately by gender (male/female), AF type (persistent/long-standing persistent), and region (US/non-US). Due to the small number of expected peri-procedural strokes, the study is not powered for these subgroup analyses, however, for these analyses, point estimates and exact one-sided 95% upper confidence intervals will be computed within each subgroup.

Additionally, if more than one PVAC catheter model (PVAC or PVAC GOLD) is used during the VICTORY AF study a subgroup analysis will be performed to assess the peri-procedural stroke rate by PVAC catheter subgroup as described in section 3.1.3.3.

## **3.3 Secondary Objectives**

### **3.3.1 Secondary Objective #1: 6-month Post-Procedural Effectiveness**

Confirm the 6-month post-procedural effectiveness.

#### **3.3.1.1 Hypothesis**

There is no pre-specified hypothesis associated with this secondary objective.

Since the 6-month effectiveness of the Phased RF system was shown to be superior to optimal medical management in the TTOP-AF study and the primary purpose of this study is to evaluate the safety of the system, there is no formal statistical hypothesis required for this objective. Thus, the main purpose for characterizing 6-month effectiveness is to demonstrate that study investigators are not overly cautious during the Phased RF procedure to optimize procedure safety.

### 3.3.1.2 Definition of 6 Month Effectiveness

6-Month effectiveness will be defined as:

- Acute procedural success, AND
- $\geq 90\%$  reduction in clinically significant AF/atrial flutter (AFL) by 48-hour Holter. Clinically significant AF/AFL is defined as any AF/AFL episode lasting longer than 10 consecutive minutes in duration, AND
- Off amiodarone for at least 90 days and off all other class I and class III antiarrhythmic drugs for at least 60 days prior to the 6-month Holter, AND
- Free from direct current (DC) cardioversion for AF for at least 60 days prior to the 6-month Holter

### 3.3.1.3 Analysis Methods

Acute effectiveness for each subject will be determined as described in section 3.3.2.2. In order for a subject to meet the acute procedural success criterion for the 6-month effectiveness endpoint, the subject must be an acute procedural success for their index and reablation procedure (if required). Holter recordings will be completed at the baseline and 6-month post final Phased RF ablation procedure. Holter recordings will be read and summarized by the Holter core laboratory. For the baseline and 6-month post-ablation procedure Holter recording, the percentage of time in clinically significant AF (AF > 10 minutes) will be calculated as the total number of seconds in clinically significant AF divided by the total Holter recording time in seconds. The percent reduction from baseline will be calculated as the difference of the percentage of time in clinically significant AF between the baseline and 6-month post-ablation procedure visit divided by the percentage of clinically significant AF at baseline. Subjects with at least a 90% reduction in clinically significant AF will be considered successful for the Holter component of 6-month effectiveness endpoint. Adjustments to all cardiovascular medications including antiarrhythmic drugs and dates of all DC cardioversions will be captured on the case report forms.

Only those subjects that have a baseline and 6-month post-procedure 48-hour Holter data that are readable by the core lab or are missing Holter data but were 6-month effectiveness failures based on other criteria at the time of the visit cutoff date will be included in the analysis of this objective. Specifically, the denominator for the 6-month effectiveness rate will include all subjects that had at least one Phased RF ablation procedure where an investigational catheter was deployed into the left atrium (i.e. placed in the left atrium and phased RF energy delivered) and have baseline and 6-month Holter data available or do not have Holter data available but were 6-month effectiveness failures based on other criteria. The numerator will include all subjects in the denominator that meet all four 6-month effectiveness conditions. A two-sided 95% exact confidence interval for 6-month effectiveness rate will be calculated.

[REDACTED]

[REDACTED]

[REDACTED]

[REDACTED]

[REDACTED]

[REDACTED]

[REDACTED]

[REDACTED]

[REDACTED]

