12.3.1.4 Analysis Methods

Acute effectiveness for each subject will be determined as described in section 12.3.2. In order for a subject to meet the acute procedural success criterion for the 6-month effectiveness endpoint, the subject must be an acute procedural success for their index and reablation procedure (if required). Ambulatory ECG monitor recordings will be completed at the baseline and 6-month post final Phased RF ablation visit. Ambulatory ECG recordings will be read and summarized by the Holter core laboratory. For the baseline and 6-month post-ablation procedure ambulatory ECG recording, the percentage of time in clinically significant AF (AF > 10 minutes) will be calculated as the total number of seconds in clinically significant AF divided by the total analyzable ambulatory ECG monitor recording time in seconds. The percent reduction from baseline will be calculated as the difference of the percentage of time in clinically significant AF between the baseline and 6-month post-ablation procedure visit divided by the percentage of clinically significant AF at baseline. Subjects with at least a 90% reduction in clinically significant AF will be considered successful for the ambulatory ECG component of 6-month effectiveness endpoint. Adjustments to all cardiovascular medications including antiarrhythmic drugs and dates of all DC Cardioversions will be captured on the case report forms.

Only those subjects that have a baseline and 6-month post-procedure 48-hour ambulatory ECG monitor data that are readable by the core lab or are missing ambulatory ECG data but were 6-month effectiveness failures based on other criteria at the time of the visit cutoff date will be included in the analysis of this

objective. Specifically, the denominator for the 6-month effectiveness rate will include all subjects that had at least one Phased RF ablation procedure where an investigational catheter was deployed into the left atrium and have baseline and 6-month ambulatory ECG monitor data available or do not have ambulatory ECG data available but were 6-month effectiveness failures based on other criteria. The numerator will include all subjects in the denominator that meet all four 6-month effectiveness conditions. A two-sided 95% exact confidence interval for 6-month effectiveness rate will be calculated.

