## Statistical Analysis Plan

Version 2  
18 July 2013

[figure not shown]
Document Change History			
Version	Version Date	Description of and Rationale for Change	Effects on Other Documents
1	28 March 2013	Initial Release	NA
2	18 July 2013	

• Updated to align with version 5 of the VICTORY AF clinical investigational plan

• Added subgroup analysis by PVAC catheter type if more than one PVAC model is used during study

• Clarified that “at least one Phased RF catheter deployed into the left atrium” means that a Phased RF catheter is placed in the left atrium and Phased RF energy is delivered

• Corrected grammatical and typographical errors

	None

---

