### **3.1.2 Summary of Ablation Procedures**

A summary of Phased RF ablation procedure information including procedure times, ablation locations, Phased RF ablation catheters used, and ablation energy modes will be summarized for procedures where at least one Phased RF ablation catheter was placed in the left atrium with Phased RF energy delivered.

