### **3.3.2.3 Analysis Methods**

All ablation procedure parameters will be captured on the case report forms. For estimating the acute success rate, all subjects with an attempted ablation where at least one of the Phased RF catheters were deployed into the left atrium (i.e. placed in the left atrium and Phased RF energy delivered) will be included in the denominator. The numerator will include all subjects in the denominator who met all the conditions for acute procedural success defined above. A two-sided 95% exact confidence interval for the acute procedural success rate will be calculated. Subjects that have a reablation attempt will be considered acutely successful if they meet all the conditions for their index procedure and conditions 1 and 4 of the acute success definition for their reablation

attempt since the source of recurrent AF will be unknown. SAS code similar to the PROC FREQ statements in section 3.3.1.3 will be used to compute the two-sided 95% exact confidence interval for the acute success rate.

In addition to calculating the acute success rate on a per subject basis, the acute success rate will be calculated on a per procedure basis. The denominator for the per procedure rate will be all Phased RF procedures where at least one Phased RF catheter was deployed into the left atrium and Phased RF energy delivered. The numerator will be all Phased RF procedures in the denominator that meet the acute success definition. A two-sided 95% confidence interval for this rate will also be calculated using the method of Rao and Scott for clustered binary data since subjects may have up to two ablation procedures. A SAS macro to calculate the Rao and Scott confidence interval can be found in the directory:

V:\AF Solutions\VICTORYAF\Documents\Statistical\_Analysis\_Plan.

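### The SAP's energy-delivered condition drops subjects with a catheter placed but no RF at any procedure from the per-subject 6-month and acute success rates, although they are failures

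*SAP*

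**What the plan says.** The Protocol's 6-month denominator (12.3.1.4) starts from "all subjects that had at least one Phased RF ablation procedure where an investigational catheter was deployed into the left atrium", with no mention of energy. Its acute success denominator (12.3.2.4) likewise asks only for an attempted ablation with a Phased RF catheter deployed.

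The SAP adds a condition in three places:
- 6-month effectiveness (3.3.1.3): "deployed into the left atrium (i.e. placed in the left atrium and phased RF energy delivered".
- Acute success per subject (3.3.2.3): "deployed into the left atrium (i.e. placed in the left atrium and Phased RF energy delivered) will be included in the denominator".
- Acute success per procedure (3.3.2.3): "all Phased RF procedures where at least one Phased RF catheter was deployed into the left atrium and Phased RF energy delivered".

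The condition is deliberate. The SAP's change history for version 2 says that deployment "means that a Phased RF catheter is placed in the left atrium and Phased RF energy is delivered".

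Both documents keep a subject without ambulatory ECG data in the 6-month denominator if the subject has already failed another component, and acute success is one of those components. The SAP (3.3.1.1) gives the main purpose of the 6-month endpoint as to "demonstrate that study investigators are not overly cautious during the Phased RF procedure to optimize procedure safety". The SAP's procedure summary (3.1.2) is also limited to procedures "where at least one Phased RF ablation catheter was placed in the left atrium with Phased RF energy delivered".

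**The concern.** An index attempt in which the catheter reaches the left atrium and no RF is given is a treatment failure by the plan's own definition. If no later procedure delivers energy either, the SAP leaves the subject out of the rate altogether. Removing only failures from a denominator pushes the rate in one direction, towards the device.

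The 6-month endpoint is there to show that safety was not bought by under-treatment. Stopping before any energy is the extreme form of that behaviour, and the energy condition removes it from view in the rate meant to detect it. The stroke endpoint is not part of this point.

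**Working it through.** **1. Does the Protocol's term mean placed?** The Protocol has no formal definition, but its usage is consistent.
- Section 12.1.1 identifies a Phased RF ablation procedure by at least one catheter placed in the left atrium.
- Table 5 and Table 10 give the same periprocedural stroke definition, one with *placed* and the other with *deployed*.
- Section 12.2.7 uses both words for one analysis cohort.
- SAP 3.2.2 itself lists the time of catheter deployment and a record of energy delivery as separate CRF items.

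**2. Is a never-energised subject a failure?** Yes.
- Acute success at the index procedure requires isolation of the pulmonary veins and use of Phased RF catheters only in the left atrium (Protocol 12.3.2.3, SAP 3.3.2.2).
- Prior left atrial ablation for AF is an exclusion criterion, so without Phased RF energy the veins have not been isolated with the study system. Using another catheter in the left atrium would breach the other condition.
- Six-month effectiveness requires acute success, so the subject fails that endpoint too and would stay in its denominator even without an ECG recording.

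**3. Who is actually lost?**
- Per-subject rates: only subjects with no energy at any procedure. A zero-energy index followed by an energised reablation stays in and counts as a failure through the index procedure.
- Per-procedure acute rate: every zero-energy procedure.

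**4. The plan's own figure.** The exact (Clopper-Pearson) 95% interval for *x* of *n* has lower limit Beta⁻¹(0.025; x, n−x+1) and upper limit Beta⁻¹(0.975; x+1, n−x).
- 110/200 = 55.0%: 47.8% to 62.0%, width 14.2 points. SAP 3.3.1.5 states 14.2% and 47.8%.
- 100/200 = 50.0%: 42.9% to 57.1%, width 14.3 points. The SAP states 14.3% and 42.9%.

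Both reproduce. At 55% the half-width is 14.2/2 = 7.1 points.

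**5. Effect on 6-month effectiveness.** With *k* zero-energy subjects restored as failures, the rate is x/(n+k). Equivalently, the SAP rate is the restored rate divided by (1−f), where f = k/(n+k). The documents give no value for *k*, so the values below are assumptions.

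| k | f | Rate | Exact 95% CI |
|---|---|---|---|
| 0 | 0% | 110/200 = 55.0% | 47.8% to 62.0% |
| 2 | 1.0% | 110/202 = 54.5% | 47.3% to 61.5% |
| 4 | 2.0% | 110/204 = 53.9% | 46.8% to 60.9% |
| 10 | 4.8% | 110/210 = 52.4% | 45.4% to 59.3% |
| 20 | 9.1% | 110/220 = 50.0% | 43.2% to 56.8% |

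It would take 20 such subjects to bring 55% down to the 50% that the plan expects to exceed.

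**6. Effect on per-subject acute success.** The documents give no acute success rate. Assuming 270/300 = 90.0% among treated subjects, 3 restored failures give 270/303 = 89.1%, 6 give 270/306 = 88.2% and 15 give 270/315 = 85.7%.

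**7. Per-procedure acute rate.** SAP 3.3.2.2 needs only conditions 1 and 4 for a reablation: Phased RF catheters only in the left atrium, and sinus rhythm at the end, with cardioversion allowed. A zero-energy reablation can meet both. Dropping it then removes a success, while dropping a zero-energy index attempt removes a failure. The net direction for this rate is not fixed.

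**The case against.** The strongest reply is that the definition was pre-specified and openly recorded, and that Protocol section 12 leaves data-handling rules to the SAP. That is true. It makes the change legitimate in form, but it still alters who is counted in rates the Protocol describes differently, and in one direction for the per-subject rates.

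A reader might infer more than the documents support:
- *That every rate can only rise.* This fails for the per-procedure acute rate, as step 7 shows. A rule making every zero-energy attempt a failure would also contradict the reablation definition in SAP 3.3.2.2.
- *That these attempts vanish from all reporting.* The SAP's baseline summaries still include a cohort defined by placement alone, so comparing cohort sizes would largely expose never-energised subjects. Protocol 12.1.2 summarises procedures on placement. A malfunction that prevents delivery can be a reportable device deficiency. Parts of both documents are redacted, so absence elsewhere cannot be established. What does stand is that the visible rates do not count these subjects as failures, the 6-month tipping-point analysis addresses missing ECG data only, and Protocol 10.1 does not treat an incomplete procedure as an adverse event unless injury occurs.
- *That the excluded subjects are the over-cautious cases.* Other causes are possible. The Protocol bars ablation below a stated ACT level (1.14, 7.9.2), so some zero-energy attempts may reflect compliance. Under-treatment with some energy stays in the denominator.
- *That the over-caution purpose is stated for both endpoints.* It is written for 6-month effectiveness only; acute success shares it as a component.

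**Conclusion.** The point holds for the two per-subject rates. The SAP removes subjects who are failures under the plan's own definitions, so those rates can only be the same or higher than under the Protocol's wording, and the check on over-caution is weaker.

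The size is unknown and probably modest. If zero-energy subjects make up about 1% to 5% of the denominator, a 55% 6-month rate is overstated by about 0.5 to 2.6 points (55.0 − 54.5 and 55.0 − 52.4), against a half-width of 7.1 points. This rests on an assumed share, on the plan's illustrative 110/200, and on reading *deployed* in the Protocol as placed, which comes from usage. Neither endpoint has a hypothesis or success threshold, so a reader should not infer that a trial decision would change. This is an inexpensive improvement to an uncontrolled descriptive estimate.

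**What to change.** - In SAP 3.3.1.3 and 3.3.2.3, base the per-subject 6-month and acute success denominators on placement of a Phased RF catheter in the left atrium. The 6-month rules on ECG data otherwise stay as they are.
- State that an index attempt with placement but no energy is an acute procedural failure and hence a 6-month failure.
- In the per-procedure acute rate, include zero-energy index attempts as failures. Report zero-energy reablation attempts separately, because conditions 1 and 4 of SAP 3.3.2.2 could otherwise count them as successes.
- Keep the energy-delivered set as a sensitivity analysis.
- In the SAP 3.1.2 procedure summary, list the number of zero-energy attempts and the reasons for them.
- Align the wording of the Protocol and SAP for these two endpoints.

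The cost is SAP text. SAP 3.2.2 shows that deployment time and energy records are already on the CRF, so the attempts can be identified. The documents do not say whether the reason is recorded, so that item may need site queries. The downside is that both rates may be slightly lower.
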